1.2 Secondary Aims

- 1.2.1 To determine the investigator- assessed objective response rate of pazopanib in children, adolescents, and young adults (patients) with relapsed or refractory solid tumors of the following types (each defining a cohort):
 - 1. osteosarcoma,
 - 2. neuroblastoma (measurable),
 - 3. neuroblastoma (evaluable), or
 - 4. hepatoblastoma

- 1.2.2 To further define and describe the toxicities of oral pazopanib in patients with recurrent/refractory solid tumors.
- 1.2.3 To further characterize the pharmacokinetics (PK) of pazopanib after administration of the powder suspension formulation in children, adolescents and young adults with cancer
- 1.2.4 To determine progression free- survival in patients with relapsed or refractory solid tumors, per cohort (described under Section 1.1.1 and 1.2.1).
- 1.2.5 To determine the time to progression in patients with relapsed or refractory solid tumors, per cohort (described under Section 1.1.1 and 1.2.1).
- 1.2.6 To determine the therapeutic activity (a confirmed complete or partial response or stable disease for at least 4 cycles) per cohort (described under Section 1.1.1 and 1.2.1).
- 1.2.7 To assess duration of response in patients with relapsed or refractory solid tumors, per cohort.
- 1.2.8 To further examine the biologic relationship between tumor response and angiogenic cytokines.
- 1.2.9 . To assess the genotype/phenotype relationships of VEGF or other members of the VEGF signaling pathway in children with soft tissue sarcoma.
 - 1.2.10 To further explore pazopanib pharmacokinetic/pharmacodynamic relationships with biomarkers and clinical outcomes, including hypertension.
 - 1.2.11 To assess overall survival (OS) in patients with relapsed or refractory solid tumors per cohort (described under Section 1.1.1 and 1.2.1).

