2.4 Pediatric Studies

2.4.1 Pediatric Phase I Studies

The Children's Oncology Group (COG) conducted a phase I study of pazopanib in children with STS or other refractory solid tumors (ADVL0815). This study was performed to determine the maximum tolerated dose (MTD) of two formulations of oral pazopanib; to define and describe the toxicities, pharmacodyamics and pharmacokinetics (PK) of pazopanib administered as a tablet (Part 1) or powder suspension (Part 2a); and to explore pazopanib induced changes in tumor blood volume and vascular permeability (Ki) using dynamic contrast enhanced MRI (DCE-MRI) in a subset of patients with STS (Part 2b). During part 1, pazopanib (tablet formulation) was administered once daily in 28 day cycles at 4 dose levels (275 to 600 mg/m²) using the rolling-six design. Dose determination for a powder suspension (Part 2a) was initiated at 50% of the MTD for the intact tablet. Ten patients with STS underwent DCE-MRI scanning at baseline and 15 ± 2 days after initiation of pazopanib at the tablet MTD (Part 2b). A total of 53 patients were enrolled; 51 were eligible [26 male, median age 12.9 yrs (range 3.8-23.9)].

Hematologic and non-hematologic toxicities were generally mild. Diarrhea, nausea, vomiting, fatigue, proteinuria and hypertension were the most commonly reported side effects. Only cycle 1 DLTs were considered for determination of the MTD and included Grade 3 lipase, amylase and ALT elevation, proteinuria and hypertension. One patient with occult brain metastasis in the imaging expansion cohort also had Grade 4 intracranial hemorrhage. The MTD was 450 mg/m²/dose for tablets, and 160 mg/m²/dose for powder suspension; two isolated and reversible Grade 3 ALT elevations were seen at the powder suspension dose of 225 mg/ m²/dose. Toxicities requiring dose modification and/or discontinuation in later cycles included tumor pain (n=2), ALT elevation (n=2), diarrhea, myalgia associated with microangiopathic hemolytic anemia, hand foot syndrome, weight loss, fistula formation at a site of prior RT, growth plate abnormality and recurrent neutropenia (each n=1). Three of 27 patients treated at the MTD had asymptomatic decreases in left ventricular systolic function; all were reversible and the drug was successfully reintroduced in two. Asymptomatic sinus bradycardia was noted in 4 patients, all ≥ 12 years. No QTc prolongation was observed.

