Serum K⁺, Ca^{++} , Mg^{++} , phosphate levels should be monitored given the risk of prolonged QTc. If serum Ca^{++} is abnormal, ionized calcium should be obtained and interventions based on ionized calcium only.

Pazopanib should be held and an EKG obtained for

- Hypokalemia or hyperkalemia \geq Grade 2
- Hypocalcemia or hypercalcemia \geq Grade 3
- Hypophosphatemia or hyperphosphatemia \geq Grade 3
- Hypomagnesemia or hypermagnesemia \geq Grade 3

These laboratory values should be corrected as soon as possible in a manner consistent with good medical judgment. Pazopanib may be resumed at a reduced dose when:

- Hypokalemia or hyperkalemia is Grade 1 or within institutional limits
- Hypocalcemia or hypercalcemia is \leq Grade 2
- Hypophosphatemia or hyperphosphatemia is \leq Grade 2
- Hypomagnesemia or hypermagnesemia is \leq Grade 2.

Even though pazopanib administration is allowed at these lower laboratory toxicity grades, every effort should be made to correct the abnormal lab values to normal if possible.

5.4.5 Proteinuria:

- If urinalysis shows ≥ trace protein then obtain a urine protein: creatinine ratio (UPC).
- If the UPC is \geq 1, then obtain a 24-hour urine collection for protein estimation.
- If the urine protein is ≥ 3.5 g/24-hours then hold pazopanib and reassess urine protein weekly.
- If the urine protein decreases to < 3.5 g/24 hours in < 21 days then resume pazopanib at a reduced dose.
- Monitor the 24 hour urine protein or UPC weekly for 2 consecutive weeks once pazopanib is resumed.
- If pazopanib is held for ≥ 28 days then the patient must be removed from protocol therapy.
- 5.4.6 Cardiac Function:

5.4.6.1 Left Ventricular Systolic Dysfunction:

Adverse events & descriptions	Dose Modifications & Evaluations
LV EF <lln <math="" but="">\geq 50% OR</lln>	Continue drug and repeat Echo on Day 28 of
LV SF \leq LLN but \geq 24% without symptoms	subsequent cycle
of cardiac dysfunction	
LV EF 40 – 49% OR	Hold pazopanib and obtain repeat Echo in 7
LV SF 15 – 23% OR	days. If toxicity confirmed, then remove
Absolute decrease in SF \geq 8 percentage	from protocol therapy.
points from baseline	If not confirmed, then resume drug at reduced
	dose and repeat Echo 14 and 28 days after
	resuming pazopanib. If any 2 Echos
	demonstrate LV EF 40 - 49% OR LV SF 15 -
	23%
	$OR \ge 8$ percentage point decrease in SF then
	remove from protocol therapy and refer to
	pediatric cardiologist
Grade 3 LV EF decreased OR	Remove from protocol therapy – refer to

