## 9.2.10. Cardiac Scan Modalities (ECHO/MUGA)

The same modality (ECHO or MUGA) for determining cardiac scan data (e.g., left ventricular ejection fraction (LVEF)) should be used to follow a subject throughout the study. The absolute change from baseline values will not be calculated for any subjects where the post-baseline value was determined by a cardiac scan modality that is different than the one used to determine baseline value.

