### 9.4.4. Left Ventricular Ejection Fraction

The following criteria will be used to flag left ventricular ejection fraction (LVEF) values that are values of potential clinical importance:

To identify LVEF values of potential clinical importance, NCI-CTCAE v4.0 will be used to assign categories that align with the grades for 'Ejection fraction decreased'.

LVEF Parameter	Potential Clinical Importance (PCI) Range	Unit
Absolute change from	• No change or any increase	%
baseline LVEF	Any decrease	
	$\circ$ >0-<10 decrease	
	○ 10-19 decrease	
	$\circ \geq 20$ decrease	
	○ $\geq$ 10 decrease and $\geq$ LLN	
	$\circ \geq 10$ decrease and below LLN	
	○ $\geq$ 20 decrease and $\geq$ LLN	
	$\circ \geq 20$ decrease and below LLN	
Relative change from	• $\geq 20$ decrease and $\geq LLN$	%
baseline LVEF	• ≥20 decrease and below LLN	

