#### ECG

A summary of the number and percentage of subjects who had normal and abnormal (clinically significant and not clinically significant) ECG findings will be displayed by scheduled visits as well as for the worst case post-baseline.

All ECG summaries will include assessments performed no later than 28 days after the last date of study drug. All ECG assessments will be listed, and those collected later than 28 days after study drug discontinuation will be flagged in the listing.

The number and percentage of subjects with clinically notable ECG values will be presented by cohort. The clinically notable ECG criteria are provided in Section 9.4.2.

For each of the QTc and QT intervals, shift tables based on notable parameter categories ( $<450, 450 - <480, 480 - <500, \ge 500$  ms) and normal range at baseline and the worst postbaseline value observed will be produced.

The changes in QTc values will be categorized into the clinical concern ranges which are specific to changes in QTc: 31-60 and >60 msec. A summary of change in QTc value will display the number and percentage of subjects with a change within each range at each scheduled assessment time and in the worst case post-baseline assessment. Subjects with missing baseline values will be excluded from this summary.

Unscheduled ECG measurements will be used in the analysis of notable ECG changes and the shift table analysis of notable QT parameters for the worst case post baseline assessment.

Listings of abnormal ECG findings and a listing of ECG values will be provided. **LVEF** 

Absolute change from baseline in LVEF will be summarized at each scheduled assessment time and in the worst case post-baseline. Only the post-baseline assessments that used the

same method (ECHO or MUGA) as the baseline assessments will be used to derive the change from baseline. The change from baseline will be categorized as follows:

- Any increase
- No change
- Any decrease:
  - 0 <10% Decrease
  - 10 <20% Decrease
  - $\circ \geq 20\%$  Decrease
- $\geq 10\%$  decrease and  $\geq LLN$
- $\geq 10\%$  decrease and < LLN
- $\geq 20\%$  decrease and  $\geq LLN$
- $\geq 20\%$  decrease and < LLN

LVEF results will also be listed with subject level details including absolute change from baseline.

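### The SAP tabulates LVEF only as change from baseline, so no LVEF table counts children who reached the 40-49% level at which the protocol holds drug

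*SAP*

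**What the plan says.** SAP 11.8 plans one LVEF summary: "Absolute change from baseline in LVEF will be summarized at each scheduled assessment time and in the worst case post-baseline". Its rows are any increase, no change, and decreases of under 10, 10 to under 20, and 20 or more. Falls of at least 10 and at least 20 are also split by whether the value is below LLN. SAP 9.4.4 has the same structure, with rows such as a fall of at least 10 points ending in "decrease and below LLN", and adds a relative fall of at least 20% split by LLN. Its opening sentence says the categories will be aligned with the CTCAE v4.0 grades for decreased ejection fraction. Neither section has an absolute EF band.

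Protocol 5.4.6.1 acts mainly on level:

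- EF below LLN but at least 50%, or shortening fraction (SF) below LLN but at least 24%, without symptoms: "Continue drug and repeat Echo on Day 28 of" the next cycle.
- EF 40-49%, or SF 15-23%, or an SF fall of at least 8 points: "Hold pazopanib and obtain repeat Echo in 7" days. The child is removed from therapy if the finding is confirmed and resumes at a reduced dose if it is not.
- "Grade 3 LV EF decreased OR" the same grade for SF: remove from therapy. No percentage is given.

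On method, SAP 9.2.10 says one modality "should be used to follow a subject throughout the study", and change is not calculated across modalities. SAP 11.8 also lists every LVEF result by subject.

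**The concern.** A secondary aim in Protocol 1.2.2 is "To further define and describe the toxicities of oral pazopanib in patients with recurrent/refractory solid tumors". Left ventricular function is a known question for this drug in children. Protocol 2.4.1 reports: "Three of 27 patients treated at the MTD had asymptomatic decreases in left ventricular systolic function". All three decreases were reversible, and drug was successfully reintroduced in two.

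A reader of the final report will want to know how many children reached the level at which the protocol stops dosing for cardiac function. The planned LVEF rows cannot answer that. A small fall from a low-normal baseline into the hold band looks like the mildest decrease, while a large fall that stays normal looks worse. The SAP handles other safety measures by level: QTc bands and vital signs have shift tables in 11.8, and laboratory values have graded shift tables in 11.7. LVEF has none, despite the stated intention in 9.4.4 to follow grades.

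What is at stake is the clarity of one descriptive safety output.

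**Working it through.** The plan states no figure for this point, so the check passes possible EF values through the planned rows.

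**Inputs.** The rows come from SAP 11.8 and 9.4.4 and the hold band of 40-49% from Protocol 5.4.6.1. Protocol 3.2.8.4 admits a child on SF of at least 27% by echocardiogram or EF of at least 50% by radionuclide scan. A baseline EF of 50% or more is therefore eligible, and the echo route states no EF floor. The documents give no LLN and no baseline EF distribution, so LLN is assumed at 50, 53 or 55% and EF is taken in whole points.

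**Falls of under 10 points into the hold band.** For baseline B, the values concerned are those from B − 9 up to 49.

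| Baseline EF | Hold values reached by a fall of 1-9 points | Number of the 10 values 40-49% |
|---|---|---|
| 50% | 41-49% | 9 |
| 55% | 46-49% | 4 |
| 58% | 49% | 1 |
| 59% or above | none | 0 |

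All of these land in the under-10 row, which has no LLN split. It is the same row that holds a fall from 51% to 50%. The relative rows in 9.4.4 do not catch them: the largest relative fall is 9/50 = 18%, below 20%.

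**All hold values.** Take whole-point baselines 50-75%. There are 26 × 10 = 260 pairs ending in 40-49%. They fall into three groups of rows:

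- 45 pairs in the under-10 row;
- 100 pairs in the 10-to-under-20 row, and in the row for at least 10 and below LLN;
- 115 pairs in the 20-or-more row, and in both below-LLN rows.

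Under each assumed LLN, every one of these groups also contains values outside 40-49%. With LLN 53 or 55%, the 100-pair group also holds 60% to 50%, a level at which drug continues in a child without symptoms. With LLN 50% it holds no value of 50% or more, but it does hold 50% to 31%. No row or combination of rows isolates the band, so the count cannot be recovered from the table.

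These are counts of possible values, not of children, and carry no probability.

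**Shortening fraction.** SAP 11.8 and 9.4.4 contain no SF row. The two SF routes to a hold are therefore untabulated.

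**Phase I context.** 3/27 = 11.1% (exact 95% CI 2.4% to 29.2%). This is the rate of any asymptomatic decrease. Its degree is not stated, so it is not a hold-band rate.

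**The case against.** The strongest reply is that the information is available elsewhere.

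- A hold-band value triggers an interruption, then removal or a reduced dose. SAP 11.5 tabulates adverse events leading to each of these.
- SAP 11.2 gives a DLT summary and listing.
- SAP 11.1 lists interruptions and reductions with reasons.
- SAP 9.5 summarises reasons for discontinuation.
- SAP 11.8 lists every LVEF value.

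SAP 4.3 records that the study was stopped after stage 1, which was 10 patients per cohort by design, with two more rhabdomyosarcoma patients noted in SAP 4.2. One listing of that size is easily read. This stands as partial cover and is the main reason the point carries little weight. It does not supply the count. Under Protocol 11.1 an abnormal scan is an adverse event only if the investigator judges it clinically significant. An interruption table by preferred term does not separate an EF hold from an SF hold. The listing has to be counted by hand.

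A second reply is that 9.4.4 offers its change rows as grade-aligned. The documents do not reproduce the CTCAE definitions, so I do not claim that the rows misstate the grades. The claim is narrower: no row carries an absolute level, and the protocol acts on one.

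A reader might infer that cardiac toxicity would go unseen, or that children would be dosed when they should be held. The documents do not support that: the hold is made at the site under Protocol 5.4.6.1, whatever the SAP tabulates. A reader might also infer that scans by a different method are lost. They are listed, and there may be none, because SAP 9.2.10 asks for one modality and the protocol schedules echocardiograms.

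**Conclusion.** The point holds as a reporting gap of low weight. No planned LVEF table counts children at the EF hold threshold, and the SF hold criteria are not tabulated. For a baseline of 50-58%, a hold-band value can appear as the mildest decrease. From 59% upward it appears as a fall of at least 10 points, pooled with values outside the band.

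The number of children affected is unknown and may be zero, and the phase I rate cannot supply it. The under-10 result rests on whole-point EF and the stated bands. The pooling examples also rest on the assumed LLN values. Reading the protocol's Grade 3 as EF below 40% is a further assumption, taken from the order of its bands, because the protocol gives no figure. No endpoint, decision rule or dosing action changes.

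**What to change.** Keep the within-method change table. Add to SAP 11.8 one shift table from baseline to worst on-therapy absolute LVEF, with these bands: at or above LLN; below LLN but at least 50%; 40-49%; below 40%. Label the last cut-off as an assumed reading of the protocol's Grade 3. Use children with at least one post-baseline LVEF as the denominator.

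Where SF is recorded, add the matching bands: at or above LLN; below LLN but at least 24%; 15-23%; below 15% (labelled as assumed). Add a row for an SF fall of at least 8 points. Without the SF rows, children held on SF alone would still be missed.

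Flag the scan method, and state how many scans the change table leaves out for method mismatch.

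The cost is a little extra programming on data already collected. The table may mix echo and MUGA values, which is why the method flag is needed.

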# 12. Pharmacokinetic Analyses

# 12.1. Sampling Schedule

All subjects will have pre-dose blood samples on Cycle 1 Day 1 and Cycle 1 Day 15 and a 3-4 hours post-dose sample on Cycle 1 Day 15 collected for analysis of pazopanib plasma concentration. Pre-dose blood sample will be collected on every subsequent odd-numbered cycle (Cycles 3, 5, etc.).

Extended PK sampling will be done during Cycle 1 in the first subjects who receive the powder suspension formulation, until 6 subjects are considered evaluable for the PK analysis. These subjects will have a blood sample for analysis of the plasma pazopanib concentration collected at the following time points on both Cycle 1 Day 1 and Cycle 1 Day 15: pre-dose and at 30 min, 1 hour, 2 hours, 4 hours, 6 hours, and 8 hours after the dose.

# 12.2. Pharmacokinetic Analysis

The PK and PKES population will be used for listings and summaries. The PKES population will be used for the figures.

Pazopanib concentrations will be listed by dose and cohort. Summary tables for PK and PKES populations for pazopanib concentrations will be presented by cycle/day, dose, and cohort. Similar summary tables of pazopanib concentrations will be presented by cycle/day and dose combining data from all cohorts. The following summary statistics for pazopanib plasma concentrations will be calculated: n, median, minimum, maximum, arithmetic mean, CV% mean, standard deviation, geometric mean, CV% geometric mean.

Steady state trough plasma pazopanib concentrations will be determined for all subjects in the PK population. A concentration will be considered to be at steady state if the subject has taken 10 consecutive daily pazopanib doses without a dose reduction or interruption. A pre-dose concentration will be considered a trough sample if collected between 22-26 hours after the previous dose of pazopanib. Concentrations which are not at steady-state will be listed and flagged but excluded from summary tables for steady state concentrations. Similarly, concentrations which are not considered trough (blood sample taken after dosing or outside window 22-26 hours after previous dose) will be listed and flagged but excluded from summary tables.

The change in steady state trough plasma pazopanib concentrations will be characterized at the first cycle and each odd cycle after the first. The effect of cycle on change in steady-state plasma trough concentrations for each cohort will be assessed for each dose graphically by plotting median steady state trough concentrations against Cycle number.

If no substantial effect of the cycle is observed, steady-state trough concentrations will be combined for all sampling occasions and summarized by dose and cohort. Similar summary table will be presented by dose combining data from all cohorts.

A summary table summarizing pazopanib concentrations at each sampling occasion and a figure for pazopanib concentrations versus time by sampling occasion (Cycle 1 Day 1 and Cycle 1 Day 15) will be generated using PKES population combining data from all cohorts.

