- 4.5.4 Concomitant administration of pazopanib with esomeprazole decreases the bioavailability of pazopanib by 40% (AUC and Cmax). Co-administration of pazopanib with Proton Pump Inhibitors (PPIs) should be avoided. Co-administration of pazopanib with PPIs is PROHIBITED from 24 hours before the first dose of pazopanib until after the final PK blood sample is collected on Day 15 ± 1 day of Cycle 1. After this, if the concomitant use of a proton-pump inhibitor (PPI) is medically necessary, it is recommended that the dose of pazopanib be taken without food once daily in the evening concomitantly with the PPI (Section 4.8). If the concomitant administration of an H2-receptor antagonist is medically necessary, pazopanib should be taken without food at least 2 hours before or at least 10 hours after a dose of an H2-receptor antagonist. Pazopanib should be administered at least 1 hour before or 2 hours after administration of short-acting antacids.
- 4.5.5 Concurrent Anti-Hypertensive Therapy: The algorithm in Section 5.4.1 will be used to grade and manage pazopanib related hypertension. Should initiation of anti-hypertensive therapy be required, single agent therapy (commonly including the calcium channel blockers amlodipine or nifedipine) may be started without notifying the study chair.

- 4.5.6 Anti-inflammatory and anti-platelet agents (e.g. aspirin, and/or ibuprofen, or other NSAIDs) could result in elevated blood pressure or increased bleeding episodes when co-administered with pazopanib and therefore should be used with caution.
- 4.5.7 Patients' medications should be reviewed at eligibility, before treatment initiation, and during treatment. Any concomitant medications that are "generally accepted" to cause a risk of Torsade de pointes are prohibited (see Appendix IIIB). Those "associated" with a risk of QTc prolongation and/or Torsades de pointes should be discontinued or replaced with drugs that do not carry these risks, if possible. Patients who must take these medications should be watched carefully for symptoms of QTc prolongation, such as syncope. Performing additional EKGs on patients who must take one or more of these medications is recommended but not required, at the investigator's discretion.

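### Troughs are compared and pooled across cycles with no account of proton pump inhibitor use, which the protocol bars up to the Cycle 1 Day 15 sample but not afterwards

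*SAP*

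**What the plan says.** **Protocol 4.5.4** gives the interaction: "Concomitant administration of pazopanib with esomeprazole decreases the bioavailability of pazopanib by 40% (AUC and Cmax"). Its general advice is that "Co-administration of pazopanib with Proton Pump Inhibitors (PPIs) should be avoided". The outright ban has an end date: co-administration with "PPIs is PROHIBITED from 24 hours before the first dose of pazopanib until after the final PK blood sample is collected on Day 15" of Cycle 1, plus or minus one day. The section then goes on: "After this, if the concomitant use of a proton-pump inhibitor (PPI) is medically necessary, it is recommended that the dose of pazopanib be taken" in the evening, without food, together with the PPI. Protocol 4.8 repeats the time-limited ban.

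**Protocol 7.3.2** schedules trough samples on Cycle 1 Day 15 and before every later odd-numbered cycle, none being required beyond Cycle 11.

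**SAP 12.2** sets two conditions for a steady-state trough. On dosing, a sample "will be considered to be at steady state if the subject has taken 10 consecutive daily pazopanib doses without a dose reduction"; an interrupted course also rules it out. On timing, a pre-dose sample counts as a trough if taken 22 to 26 hours after the previous dose. Samples failing either condition are listed, flagged and left out of the summaries. The comparison over time is a plot of medians: "The effect of cycle on change in steady-state plasma trough concentrations for each cohort will be assessed for each dose graphically". If no substantial cycle effect appears, troughs from all occasions are combined by dose and cohort.

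**SAP 12.3.1** combines all occasions again by age subgroup, unless a cycle effect has been identified. **SAP 12.4** compares troughs with 20.5 µg/mL using each subject's first steady-state trough. **SAP 12.5** relates trough to clinical benefit and to hypertension without saying which trough is used. The SAP does not mention PPIs or other acid-reducing drugs.

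**The concern.** The Day 15 trough is free of PPIs by rule; the troughs from Cycle 3 onward need not be. A drug that the protocol itself says reduces exposure can therefore be present on one side of the cycle comparison and not on the other. By ending the ban at a PK sample, the protocol shows that it regards PPI use as relevant to the PK data, but the analysis plan does not carry this forward.

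Two outputs are exposed. The first is the plot by cycle: PPI use after Day 15 could look like a fall in trough over time, or could cancel a real rise. The second is the pooled summaries, overall and by age subgroup, which would contain PPI-lowered values if the plot suggests nothing. The same plot decides whether pooling goes ahead, and it has no numerical criterion.

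**Working it through.** **1. Is PPI use tied to cycle, and does the SAP deal with it?**

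| Sample | PPI status under Protocol 4.5.4 and 4.8 | SAP 12.2 conditions |
|---|---|---|
| Cycle 1 Day 15 trough | prohibited | 10 doses without change; 22-26 h |
| Cycle 3, 5, 7, 9, 11 troughs | discouraged, possible if medically necessary | the same two, nothing on PPIs |

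The confounding follows from the rules themselves. Neither condition removes it, and the SAP plans no flag, exclusion or sensitivity analysis for it.

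**2. How large could it be?** The 40% is an imported result with no inputs in the documents, so it cannot be re-derived. It is stated for esomeprazole, and for AUC and Cmax. Neither document gives an effect on trough or the frequency of PPI use. What follows is an illustration.

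Let f be the share of later troughs taken on a PPI and r the reduction in trough on a PPI.

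- Ratio of later mean to PPI-free mean = 1 − r·f
- Ratio of geometric means = (1 − r)^f
- Ratio of medians: from a log-normal mixture fitted to the phase I troughs

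The phase I troughs are in Protocol 2.4.2: 42 ± 13 (n = 13) and 29 ± 13 (n = 27), taken as µg/mL.

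- Combined mean = (13 × 42 + 27 × 29)/40 = 1329/40 = 33.2
- Combined SD = √{[38 × 13² + 13 × (42 − 33.225)² + 27 × (29 − 33.225)²]/39} = √(7905/39) = 14.2

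With r = 40% (assumed for trough) and f assumed:

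| f | Mean | Geometric mean | Median |
|---|---|---|---|
| 5% | −2% | −2.5% | −2% |
| 10% | −4% | −5% | −4% |
| 20% | −8% | −10% | −9% |
| 30% | −12% | −14% | −13% |
| 50% | −20% | −22.5% | −22.5% |

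So each 10 percentage points of PPI use lowers the later mean by 0.4 × 10% = 4%. If only half the effect reached trough (r = 20%), that becomes 2%.

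**3. Masking.** With f = 20% and r = 40%, a true rise of 1/0.92 − 1 = 8.7% in later means would show as no change.

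**4. Pooled tables.** If later samples are a share w of all pooled samples, the pooled mean falls by r·f·w. With w = 50% (assumed), f = 20% and r = 40%, the fall is 0.4 × 0.2 × 0.5 = 4%.

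**5. After the fix.** With on-PPI samples left out, every ratio in the table returns to 1.00.

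**The case against.** The case for leaving the plan alone has several parts.

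- **The 40% may not apply to trough.** Protocol 2.4.1 reports that phase I troughs did not appear dose-dependent over 275 to 600 mg/m² and varied widely between patients. That weakens a proportional carry-over. This stands, and is why the size is left open.
- **Use may be rare.** PPIs are discouraged throughout. Patients following the evening-dosing advice may miss the 22 to 26 hour window if blood is drawn with daytime laboratory tests, and would then be excluded anyway. This stands too, but it is incidental and not a PPI rule.
- **The shift is small against the noise.** A 4% shift is slight beside a between-patient CV of 14.2/33.2 = 43%. Later troughs may also be few: the phase I median was 2 cycles, and SAP 4.3 records that the study was declared futile at the end of stage 1. SAP 12.2 also assigns figures to the extended-sampling population, planned around six evaluable patients. All true, but in a sparse plot by cohort and dose one or two PPI users can move a median.
- **The analysis is descriptive.** SAP 8.4 plans no hypothesis test, and a visible cycle effect blocks pooling. This limits the harm but does not separate PPI use from cycle.
- **An on-PPI trough is a valid measurement.** It is the exposure the patient had. This is persuasive for SAP 12.5, where exposure is related to outcome, so exclusion there is not warranted.

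A reader might go further and infer that the comparison with 20.5 µg/mL is undermined. On the phase I figures a 40% cut takes the mean to 0.6 × 33.2 = 19.9 and the share above 20.5 from about 81% to 47% under a normal distribution. That calculation puts every patient on a PPI, whereas SAP 12.4 uses the first steady-state trough, normally the PPI-free Day 15 sample. Nor does the SAP say that a fall over cycles would be reported as a property of pazopanib.

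**Conclusion.** The gap is real but modest. The protocol's time-limited ban makes PPI use differ systematically between Day 15 and later troughs, and SAP 12.2 and 12.3.1 compare and pool those troughs without accounting for it. The cycle plot, the pooled trough summaries and the age-subgroup trough summaries are exposed.

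The size cannot be stated from the documents. About 4% of the later mean per 10 percentage points of PPI use holds only if the esomeprazole effect on AUC and Cmax carries over in full to trough and to other PPIs. SAP 12.4 is affected only where a subject has no valid Day 15 trough. SAP 12.5 is open because the trough is not specified. The point concerns secondary PK outputs and has no bearing on objective response. It merits a change because the remedy is cheap.

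**What to change.** This is a change to the analysis plan only; the protocol's co-medication rules are not in question.

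- **SAP 12.2:** list and flag any trough taken while a PPI is recorded as ongoing or recently stopped, with the look-back period stated. Give a rule for missing PPI end dates, since SAP 9.2.5.2 does not impute concomitant-medication end dates.
- **SAP 12.2 and 12.3.1:** leave flagged samples out of the cycle-effect plot and the pooled trough summaries, including those by age subgroup, and show them on a separate line.
- **SAP 12.5:** keep flagged samples, say which trough is used, and add a display with and without them.

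No new data are needed: Protocol 4.4 has concomitant medications recorded in the eCRF with dates, and SAP 12.2 already lists, flags and excludes other samples. The cost is one derived flag, some SAP wording, and the loss of a few later-cycle samples from the main summaries.
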